## 2.3 Sample Size

A total sample size of 39 participants (13 per arm) in an analysis of covariance using a planned comparison between the average of the two treatment arms versus control achieves 80% power to detect a minimally important mean difference of **50 meters** in the primary outcome (6MWD) using an F-test with a two-sided 5% significance level. The SAS procedure GLMPOWER was used to conduct the calculation (SAS Institute Inc. 2008. SAS/STAT® 9.2. User’s Guide. Cary, NC: SAS Institute Inc). The common standard deviation is assumed to be 85 and the correlation between baseline and 6 months is 0.80. These estimates are similar to those observed in our PHACeT trial where the standard deviation was 80 meters and the correlation between baseline and 6 month was 0.86. To account for 10% potential attrition, we will enroll and randomize 45 subjects (15 allocated to each arm).

## 2.4 Framework

This will be a superiority trial, with primary aim to determine whether receiving a course of 4 monthly doses of eNOS-EPCs will improve the 6 minute walk distance (6MWD) at 6 months

compared to placebo. A minimally important mean difference of 50 meters was considered for this hypothesis.

## 2.5 Statistical Interim analyses and stopping guidance

**Interim Analysis:** No formal interim analysis will be conducted for efficacy. A safety analysis is planned after the first twelve participants complete primary endpoint data collection at the 6-month follow-up visit. Safety data will be sorted by treatment arms (blinded) to determine the distribution of potential safety concerns and be provided to the DSMB for review. The unblinded treatment allocation will be available from the statistician should the DSMB determine that a safety concern exists that necessitates unblinding.

**Study Stopping Criteria:** Enrolment and administration of the study product at all sites will be immediately placed on hold with the occurrence of any one of the following: i) death, ii) major cardiovascular event, or iii) a life-threatening response (i.e. immune reaction) that is deemed “definitely related” to the *study product* by the trial Data Safety and Monitoring Board (DSMB). The Chair of the DSMB will be notified promptly and be provided with copies of de-identified source information for review and will make recommendations for protocol amendments or revisions to the Investigator’s Brochure and/or the risk section of the informed consent form as required. The sponsor will inform Health Canada immediately of the “definitely-related” *unexpected and serious event* that met the predefined stopping criterion. Site investigators will be provided with the case information for reporting to their local REB. The Steering Committee may consider resuming the trial after consideration of the DSMB recommendations, and, if applicable, any submission and approval of any suggested protocol/consent amendments by Health Canada and the local REBs.

**Premature Trial Discontinuation:** Premature trial discontinuation may occur as a result of an event that triggers the protocol-defined study stopping criteria. Termination or suspension of the trial may also result from a recommendation made by the Data and Safety Monitoring Board. The Steering Committee will review any DSMB recommendations and will rule on any consequential actions to be implemented by the sponsor. If the sponsor is required to terminate or suspend the trial, the sponsor will notify the principal investigators in writing. The investigators, in turn will promptly inform their research staff, the trial participants and their local Research Ethics Board of this development. The sponsor will follow-up with the investigative sites by sending the principal investigators written instructions for participant and trial close-out procedures. The investigators in turn, should assure appropriate follow-up for the study participants. The sponsor will notify the Biologics and Genetic Therapies Directorate of Health Canada no later than 15 calendar days after the date of trial discontinuation.

The sponsor may terminate a site’s participation due lack of enrollment, concerns of data integrity, protocol noncompliance or investigator conflict of interest. If the investigator terminates or suspends the trial without prior agreement of the sponsor, the investigator will inform the institution where applicable, and the investigator/institution must promptly inform the sponsor and the REB and should provide both with a detailed written explanation of the termination or suspension.

If the Research Ethics Board (REB) terminates or suspends approval of a trial, the principal investigator will inform the institution where applicable and the investigator/institution must

promptly notify the sponsor and provide the sponsor with a detailed written explanation of the termination or suspension.

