- Physical examination by the principal investigator or sub-investigator
- Assessment of WHO functional class (see Appendix C)
- Assessment of adverse events and serious adverse events
- Vital signs
- Concomitant medication recording
- 12 lead ECG
- O₂ saturation (peripheral device)
- Laboratory tests: sodium, potassium, chloride, TCO₂, blood sugar, BUN, creatinine, calcium, magnesium, phosphorus, alkaline phosphatase, total bilirubin, CPK, troponin, AST (SGOT), ALT (SGPT), LDH, gamma GT, albumin, uric acid, CBC with differential, ESR, PT, PTT, INR (if warfarin sodium has been held for RHC procedure), BNP level, and CRP
- Additional blood samples for measurement of circulating biomarkers will be taken to be stored for no more than 15 years in the central biorepository at OHRI (no genetic testing will be performed)
- Urine pregnancy test for females with childbearing potential (to be done prior to administration of study product on the same day)
- Urine collection for routine and microscopic analysis

- 2D Echocardiogram with Doppler and saline contrast (as per echocardiography protocol)
- Cardiac MRI at sites where this is available (only for participants who are not on prostacyclin pumps and have no other exclusions for MRI such as claustrophobia) according to Cardiac MRI protocol
- PFTs [TLC, FVC, FEV₁/FVC, DLCO]
- Chest x-ray
- **6MWD test (for primary EP analysis)** and Borg dyspnea index (see Appendix D and E)
- Quality of Life Questionnaire SF-36 (see Appendix G)
- Out-patient right heart catheterization for hemodynamic assessment (BP, HR, RAP, RVP, PAP, mPAP, PAWP, PVR, SVR, CO, CI, SvO2)
 - Patients who are currently receiving anticoagulant therapy (warfarin sodium, NOAC) will be managed according to the standard procedure at participating sites
 - Cardiac output will be determined using the thermodilution (in triplicate) and/or Fick methods.

Administration of study product:

• As per section 7.1 (According to Study Product Delivery Protocol – Appendix H)

Post-treatment procedures:

• As per section 7.1 (According to Study Product Delivery Protocol – Appendix H)

7.5. Follow up/Treatment Visits: Months 7, 8 and 9 Post First Delivery of Study Product (±4 days; Can occur over 2 days)

Pre-treatment Procedures:

- Physical examination by the principal investigator or sub-investigator
- Assessment of WHO functional class (see Appendix C)
- Assessment of adverse events and serious adverse events
- Vital signs
- Concomitant medication recording

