## 4.2 Withdrawal/Follow-up

### Premature Participant Withdrawal

Premature withdrawal of study participants may be based on any of the following reasons:

- Sponsor Recommendations (i.e. Safety-specific protocol requirements)
- Investigator Decision (i.e. Participant non-compliance or if participant cannot safely perform the procedures required in the protocol)
- Participant Decision (No longer wishes to take part in the trial)
- Death of the study participant
- Pregnancy during the 12 month study treatment/follow-up period (refer to Section 9.7 for guidance)

Following the receipt of the study product, a participant may withdraw consent for study follow-up at any time for any reason. In addition, a participant may be considered withdrawn for failure to return for study visits or become lost to follow up for any other reason.

If a participant withdraws consent for further study follow-up procedures and assessments, every effort should be made to continue to follow the participant for their safety and the collection of safety data. This would ideally include completion of a treatment phase premature withdrawal visit (see Treatment Phase Premature Withdrawal Visit) and the long-term follow-up registry annual phone calls.

The PI or research staff must determine whether the participant wishes to:

- Withdraw from study follow-up procedures and assessments, but permit telephone follow-up or review of clinic/hospital records for data collection
- Withdraw from study follow-up procedures and assessments and decline further contact, however permit their accumulated data to be included in the study analysis
- Withdraw from study follow-up procedures and assessments and decline further contact and access to personal health information and indicate data collected to date cannot be used in the final analysis. Source documents cannot be destroyed until completion of the long-term storage period (25 years).

The primary reason for premature withdrawal and the participant's decision to decline study follow-up must be recorded in the participant's source documents and on the Treatment Phase Exit eCRF.

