#### Treatment Phase Premature Withdrawal Visit

In the event of early withdrawal from the 12-month treatment phase of the trial, a Premature Withdrawal visit will be completed with the following timing:

1.  $30 \pm 2$  days after the last study product injection (for participants who exit the treatment phase between Months 0-4 or 6-10)
2.  $5 \pm 2$  days following withdrawal from the treatment phase (for participants who exit the treatment phase between Months 4-6 or 10-12)

The following assessments will be performed:

- Physical exam by the principal investigator or co-investigator
- Concomitant medication recording
- Vital signs (blood pressure, heart rate, respirations)
- Assessment and recording of WHO functional class (see Appendix C)
- O2 saturation (peripheral device)
- Laboratory tests: sodium, potassium, chloride, TCO2, blood sugar, BUN, creatinine, calcium, magnesium, phosphorus, alkaline phosphatase, total bilirubin, CPK, troponin, AST (SGOT), ALT (SGPT), LDH, gamma GT, albumin, uric acid, serum ferritin, CBC with differential, ESR, PT, PTT, INR, brain natriuretic peptide (BNP), C-reactive protein (CRP)
- Urine collection for routine and microscopic analysis
- Urine pregnancy test for females with childbearing potential
- 6MWD test and Borg dyspnea index (see Appendix D and E)
- Resting 12 lead ECG
- Assessment of adverse events and serious adverse events

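### The one planned aggregate safety analysis counts Month 6 completers, so each early death or exit postpones it, with no fallback

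*SAP*

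**What the plan says.** SAP 2.5 states that "No formal interim analysis will be conducted for efficacy" and then sets the only scheduled look at accumulating safety data in either document: "A safety analysis is planned after the first twelve participants complete primary endpoint data collection at the 6-month follow-up visit". The same sentence stands in SAP 5.4 (Analysis of Safety) and Protocol 11.9. The data are to be grouped by arm under blinded labels and given to the DSMB, which can obtain the allocation if it sees a concern. Protocol 7.4 identifies the Month 6 walk as the test used for the primary endpoint.

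Participants lost before Month 6 follow a different path. "Death of the study participant" is a listed reason for premature withdrawal (SAP 4.2; Protocol 9.5). For early exit from the treatment phase, "a Premature Withdrawal visit will be completed with the following timing" (SAP 4.2; Protocol 9.8). That visit is not the Month 6 visit.

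SAP 2.5 and Protocol 9.3 also contain an event-driven route. Enrolment and product administration "at all sites will be immediately placed on hold with the occurrence of any one of the following": death, a major cardiovascular event, or "a life-threatening response (i.e. immune reaction) that is deemed" definitely related to the product by the DSMB. In addition, "The Chair of the DSMB will be notified promptly and be provided with copies of de-identified source information for review". Protocol 12.1 gives the DSMB a continuing safety remit and leaves the detail to its Terms of Reference.

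**The concern.** The trigger is an efficacy-data milestone that only participants who are alive and still in follow-up can reach. Any harm that ends in death or exit before Month 6 removes a participant from the count, and the review then waits for a later recruit. Meanwhile enrolment and dosing continue unless the separate hold applies. Neither document gives a calendar date, enrolment count, event count or rule for counting losses that would cap the wait.

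At stake is the comparison between arms. Protocol 10.5 lists right heart failure, syncope, hypotension and hypoxemia as expected in this population, so a death or withdrawal from such a cause can reasonably be put down to the disease when judged alone. An excess in the cell-treated arms would show only when events are set side by side by arm. Early losses are foreseeable: the sample size allows for 10% attrition, and one of the seven phase 1 patients died during that study (Protocol 1).

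The documents also do not say whose data enter the review. Read narrowly, it could cover only the twelve completers.

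**Working it through.** **Inputs.** Trigger: 12 completers (SAP 2.5). Randomised: 45, allowing for 10% attrition from 39 (SAP 2.3; Protocol 11.1). Recruitment: five years (SAP 2.1). Assumptions: uniform accrual, losses independent between participants, and a proportion d lost before the Month 6 walk. The documents give no rate of death or exit by Month 6. The 10% is used as a stand-in for d; the 20% and 30% values are assumptions.

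**The plan's own figures.** 39 / (1 − 0.10) = 43.3, rounded up to 44, and to 45 for three equal arms. This agrees with the plan. The 39 also reproduces: the residual SD is 85 × √(1 − 0.80²) = 51 m, and a 50 m contrast of 26 against 13 with 1 and 35 degrees of freedom gives 80.1% power. No derivation is given for the trigger of twelve.

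**Delay.**

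- Accrual = 45 / 60 = 0.75 per month, so each lost participant costs 1 / 0.75 = 1.33 months.
- Mean number randomised to obtain 12 completers = 12 / (1 − d).
- Mean time to review = [12 / (1 − d)] / 0.75 + 6 months.
- Mean delay = [12 / (1 − d) − 12] / 0.75.
- Mean number randomised by the review = 12 / (1 − d) + 6 × 0.75.

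| Early loss d | Randomised to obtain 12 completers | Time to review (months) | Delay (months) | Randomised by the review |
|---|---|---|---|---|
| 0 | 12.0 | 22.0 | 0 | 16.5 |
| 10% | 13.3 | 23.8 | 1.8 | 17.8 |
| 20% | 15.0 | 26.0 | 4.0 | 19.5 |
| 30% | 17.1 | 28.9 | 6.9 | 21.6 |

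If the first participant is taken to enter at time zero, the no-loss review falls at 11 / 0.75 + 6 = 20.7 months. The delays do not change.

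**Sensitivity to accrual.** If recruitment took three to seven years (an assumed range), the mean delay would be 1.1 to 2.5 months at 10% loss, 2.4 to 5.6 at 20%, and 4.1 to 9.6 at 30%.

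**Chance that the issue arises.** The probability that at least one of the first twelve randomised fails to complete is 1 − (1 − d)^12. At d = 10% this is 1 − 0.9^12 = 72%.

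**Who still counts.** Stopping product is not the same as leaving follow-up. Unblinded participants continue to be followed (Protocol 9.1), a missed dose leaves the visit schedule in place (7.10), and pregnant participants who have received cells stay on the schedule apart from imaging and catheterisation (9.7). These participants can still complete the Month 6 walk, so d covers mainly death and exit from follow-up.

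**The case against.** The strongest reply is that the DSMB does not depend on this review. The event-driven hold brings serious events to the Chair promptly. The DSMB judges relatedness, so it must see individual cases. It may recommend suspension or termination without a stopping criterion having been met (Protocol 9.4). Serious adverse events are reported within 24 hours (Protocol 10.8). The Terms of Reference may schedule further meetings. At the only attrition figure in the documents, the slip is under two months on a review due at about month 22.

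All of this stands, and it limits the point. A reader might infer that the more harm there is, the later the DSMB looks at anything. The documents do not support that: only the scheduled aggregate analysis slips, and only for harm that ends in death or exit from follow-up. A reader might also take the twelve to be the first twelve randomised, so that one early loss leaves the condition unmet for good. The wording allows that, but the first twelve to complete is the more natural reading.

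The reply does not remove the defect. The event route considers cases one at a time. The sentence structure leaves unclear whether the definitely-related qualifier covers all three event types or only the last, and that passage needs clarifying in its own right. If it covers all three, a death judged only possibly related triggers no hold. On either reading, withdrawals that are not themselves one of the three listed events trigger none. A meeting schedule that may exist in a document not available here does not correct the rule written in these two.

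**Conclusion.** The point holds for the scheduled aggregate safety analysis. Its trigger counts Month 6 completers, so each death or exit from follow-up before then postpones it, by about 1.33 months per loss at the assumed accrual, and nothing in either document caps the delay. The mean delay is about 1.8 months at 10% early loss, 4.0 at 20% and 6.9 at 30%. These figures rest on uniform accrual of 45 over 60 months and independent losses. The 10% is a stand-in for loss by Month 6, and the higher rates are assumptions.

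The delay is modest at the planned attrition. What makes the rule worth changing is its direction: it yields the aggregate comparison later when early losses are higher. With event-driven oversight in place, this is a cheap improvement of moderate severity and not a condition for the trial to proceed.

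**What to change.** In Protocol 11.9 and SAP 2.5 and 5.4, trigger the analysis when the first twelve randomised and dosed participants have each reached the Month 6 visit, died or exited follow-up. State that it includes safety data from every participant dosed by the cut-off, and check the wording against the DSMB Terms of Reference.

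The condition should cover all twelve participants. A rule tied to the twelfth participant alone could fire as soon as that person exited, before earlier participants had reached Month 6.

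At 0.75 participants per month, the review then falls at about month 22 at the latest, whatever the loss rate. The cost is one or two sentences in three places. The downside is that the review may include fewer than twelve Month 6 completers. Sample size and alpha are unaffected because no efficacy analysis is done at that point, and the dosing and hold rules are left as they are.

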## 2.6 Timing of final analysis

Final analyses will be conducted following the end of the trial, once 45 participants are randomized and complete the 12-month treatment phase of the trial. The data will be collected, cleaned, verified, and locked by the OHRI Methods Centre data management services (DMS) group. Final analysis will be commenced once the final lock has been confirmed by the Trial Medical Consultant or the Clinical Trial Manager. The datasets will be provided to the trial statistician who will prepare reports and models for the analysis of the trial.

## 2.7 Timing of outcome assessment

Appendix B – Schedule of Assessments

Time point Assessment	Screening phase	Treatment Phase								Registry Yearly Telephone Call x 10 (±15 days)
		Month 0	Months 1, 2, 3 (±4 days)	Month 4 (±4 days)	Month 6 (±5 days)	Months 7, 8, 9 (±4 days)	Month 10 (±4 days)	Month 12 (±5 days)	Premature Withdrawal (see Note  )	
Informed consent	X									
Eligibility Assessment	X									
Demographics, medical history	X									
Concomitant Medication Recording	X	X	X	X	X	X	X	X	X	
Physical exam by investigator	X	X	X	X	X	X	X	X	X	
WHO class	X	X	X	X	X	X	X	X	X	
Vitals signs (See Note  )	X	X	X	X	X	X	X	X	X	
Body weight & height	X									
O 2 saturation	X	X	X	X	X	X	X	X	X	

SAPPHIRE Statistical Analysis Plan

Clinical Blood Tests (See Note  )	X(a)	X(b)	X(c)	X(c)	X(b)	X(c)	X(c)	X(b)	X(b)	
Inflammatory biomarkers (See Note  )		X	X	X	X	X	X	X		
Biomarkers for storage (See Note  )		X			X			X		
Urine pregnancy test (See Note  )	X 	X 	X 	X	X 	X 	X	X	X	
Urinalysis	X	X			X			X	X	
12-Lead ECG	X	X	X	X	X	X	X	X	X	
6MWD Test (See Note  )	X(*)	X	X	X	X	X	X	X	X	
Borg Dyspnea Index (See Note  )	X	X	X	X	X	X	X	X	X	
Apheresis (See Note  )	X									
QOL Questionnaire (See Note  )		X	X 		X	X 		X		
Chest x-ray	X				X			X		
2D Echocardiogram with Doppler and saline contrast (See Note  )		X	X 		X	X 		X		
Cardiac MRI		X			X			X		
Hemodynamic Measurements		X			X			X		
PFTs		X			X			X		
Study Product Administration		X	X		X	X				
A/E & SAE Assessment		X	X	X	X	X	X	X	X	X

**NOTE:** **Vital Signs:** Blood pressure, heart rate, respirations (all measured seated after 10 minutes of rest)

**NOTE:** **Clinical Blood Tests:**

- X(a)** sodium, potassium, chloride, TCO2, blood sugar, BUN, creatinine, calcium, magnesium, phosphorus, alkaline phosphatase, total bilirubin, CPK, troponin, AST (SGOT), ALT (SGPT), LDH, gamma GT, albumin, uric acid, serum ferritin, CBC with differential, ESR, PT, PTT, INR, HIV-1/2, HBV, HCV, HTLV-I/II, *Treponema pallidum* (TP) Antibodies,  $\beta$ -hCG for females with childbearing potential
- X(b)** sodium, potassium, chloride, TCO2, blood sugar, BUN, creatinine, calcium, magnesium, phosphorus, alkaline phosphatase, total bilirubin, CPK, troponin, AST (SGOT), ALT (SGPT), LDH, gamma GT, albumin, uric acid, serum ferritin, CBC with differential, ESR, PT, PTT, INR, brain natriuretic peptide (BNP), C-reactive protein (CRP)
- X(c)** sodium, potassium, chloride, TCO2, blood sugar, BUN, creatinine, calcium, magnesium, phosphorus, alkaline phosphatase, total bilirubin, CPK, troponin, AST (SGOT), ALT (SGPT), LDH, gamma GT, albumin, uric acid, serum ferritin, CBC with differential, ESR, BNP, CRP

**NOTE:** **Inflammatory Biomarkers:** For treatment visits (Month 0-3, 6-9), samples must be drawn immediately prior to study product delivery.

**NOTE:** **Biomarkers for Storage:** Samples will be stored in the OHRI biorepository for up to 15 years.

**NOTE:** **Urine Pregnancy Test:** **X** Must be performed in the morning prior to apheresis on the same day  
**X** Must be performed prior to product administration on the same day

**NOTE:** **6MWD Test:** **X(\*)** During screening, two 6MWD tests to be performed within 24 hours with at least 1 hour of rest between the tests.

**X** One 6MWD test to be performed at all other visits

**NOTE:** **Borg Dyspnea Index:** Measured at the beginning and end of the 6MWD test

**NOTE:** **Apheresis:** To be performed within 3 months of completion of screening assessments.

**NOTE:** **QOL Questionnaire:** **X** Administered only at 3 month visit  
**X** Administered only at 9 month visit

**NOTE:** **2D Echocardiogram:** **X** Performed only at 3 month visit  
**X** Performed only at 9 month visit

**NOTE:** **Premature Withdrawal Visit:** Performed for participants withdrawn from the trial during the treatment phase:

1.  $30 \pm 2$  days after the last study product injection (for participants who exit the treatment phase between Months 0-4 or 6-10)
2.  $5 \pm 2$  days following withdrawal from the treatment phase (for participants who exit the treatment phase between Months 4-6 or 10-12)

